## 2.5.2 Management of Clinical Study Cases

Clinical judgments for management and personalized preventive treatment of study participants are based on estimates of the ratio between expected MACCE and bleeding risks, as recommended in the ESCARDIO/EACTS 2017 revised guideline for the treatment of CAD with DAPT†‡.

† - The ESCARDIO/EACTS 2017 revised guideline recommendations for the treatment of CAD with DAPT [ESC GUIDELINES] present approaches and tools for assessing the relationship between MACCE and bleeding risks.

‡ - The selection of patients for clopidogrel treatment based on the results of CYP2C19 allele genotyping is clearly stated by the FDA in the form of warnings related to the use of clopidogrel ("Black Box of Warnings"), as "reduced efficacy of clopidogrel in poor metabolizers" [FDA. PLAVIX (clopidogrel bisulfate) tablets. Initial U.S. Approval: 1997. FULL PRESCRIBING INFORMATION. WARNINGS AND PRECAUTIONS (5.1), CYP2C19 Poor Metabolizers (2.3), Pharmacogenomics (12.5). 2010.]

Ongoing management of clinical study cases and appropriate treatment, including clinical cases of all early withdrawn study participants, should be conducted following the guidelines and recommendations provided by ESCARDIO for ASCVDs group diseases, AHA for ischemic and hemorrhagic strokes, ACG for GI bleeding, and ISTH for thrombocytopenic thrombotic purpura:

- 2017 ESC focused update on dual antiplatelet therapy in coronary artery disease developed in collaboration with EACTS - doi:10.1093/eurheartj/ehx419;
- 2019 ESC Guidelines for the diagnosis and management of chronic coronary syndromes - doi:10.1093/eurheartj/ehz425;
- 2021 ESC Guidelines on cardiovascular disease prevention in clinical practice - doi:10.1093/eurheartj/ehab484;
- 2019 ESC Guidelines on diabetes, pre-diabetes, and cardiovascular diseases developed in collaboration with the EASD – doi:10.1093/eurheartj/ehz486;
- 2019 ESC/EAS Guidelines for the management of dyslipidaemias: lipid modification to reduce cardiovascular risk - doi:10.1093/eurheartj/ehz455;
- 2018 ESC/ESH Guidelines for the management of arterial hypertension - doi:10.1093/eurheartj/ehy339;
- 2017 ESC Guidelines for the management of acute myocardial infarction in patients presenting with ST-segment elevation - doi:10.1093/eurheartj/ehx393;
- 2020 ESC Guidelines for the management of acute coronary syndromes in patients presenting without persistent ST-segment elevation - doi:10.1093/eurheartj/ehaa575;
- Fourth universal definition of myocardial infarction (2018) - doi:10.1093/eurheartj/ehy462;
- 2022 ESC Guidelines for the management of patients with ventricular arrhythmias and the prevention of sudden cardiac death - doi.org/10.1093/eurheartj/ehac262;
- 2018 ESC/EACTS Guidelines on myocardial revascularization - doi:10.1093/eurheartj/ehy394;
- 2018 ESC Guidelines for the diagnosis and management of syncope - doi:10.1093/eurheartj/ehy037;
- 2017 ESC Guidelines on the Diagnosis and Treatment of Peripheral Arterial Diseases, in collaboration with the European Society for Vascular Surgery (ESVS) - doi:10.1093/eurheartj/ehx095;
- Guidelines for the Early Management of Patients With Acute Ischemic Stroke: 2019 Update to the 2018 Guidelines for the Early Management of Acute Ischemic Stroke: A Guideline for Healthcare Professionals From the American Heart Association/American Stroke Association - doi.org/10.1161/STR.000000000000211;
- 2022 Guideline for the Management of Patients With Spontaneous Intracerebral Hemorrhage: A Guideline From the American Heart Association/American Stroke Association - doi.org/10.1161/STR.000000000000407;
- 2021 ACG Clinical Guideline: Upper Gastrointestinal and Ulcer Bleeding - DOI: 10.14309/ajg.0000000000001245;
- 2020 ISTH guidelines for treatment of thrombotic thrombocytopenic purpura - doi.org/10.1111/jth.15010

Treatment of concomitant diseases/conditions should be carried out according to national protocols and recommendations. Contraindications and restrictions should be taken into account when prescribing medications.

These measures of drug treatment and management of a clinical case are routinely used in established, routine clinical practice.

### **2.5.3 Other Perspective Arms of the Study**

In the case of equal distribution of study participants by gender and inclusion of 50% more than the planned number, it will be possible to evaluate the gender-related CYP2C19 allele genotype-guided clopidogrel treatment outcomes.

The study participants' selection process will form a clinical group of CAD STE/NSTE-ASC patients who require treatment with a P2Y12 inhibitor (including clopidogrel) after PCI, characterized by a more severe course of the disease and a significantly higher baseline risk of recurrent MACCEs compared with the participants group under the study. The perspective arm is clinically more heterogeneous and requires a different study design. This group differs from the study participants group in terms of inclusion and exclusion criteria, but requires treatment with a P2Y12 inhibitor (including clopidogrel) after PCI.

The concept of study P2Y12 inhibitor preventive antiplatelet treatment of this perspective study arm cases may be based on the clinical outcomes of CYP2C19 genotype-guided drug selection. In real-world practice, the patients with primary PCI after CAD STE/NSTE-ASC are more prevalent than current study group patients. Despite their similarity to the study group, they are characterized by a significantly higher baseline risk and a more severe course of the disease. Patients of Perspective Arms of the Study are clinically more heterogeneous and require a different study design.

In the future, a study with similar goals and objectives, albeit with a different design, could be planned for this group of patients and conducted, provided the necessary resources are raised, which would be justified from a scientific point of view, clinical feasibility, and ethical considerations.

#### **2.5.4 Disclosure of Study Results**

The allocation of patients to the experimental and control groups will be carried out by double-blind randomization. At this stage, the results of the randomization will be hidden from the study participants, the medical care team, and the clinical outcome assessors. However, after randomization and CYP2C19 genotyping, the results will be disclosed to the study participants and the medical care team, and the results of both the baseline and ongoing clinical assessments of the study subject will be known throughout the study.

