The procedures of the post-analytical stage of the laboratory study include the analysis of the measurement results obtained at the RT-PCR stage, the formation of the final test result, and the documentation of the study result in the form of a report.

The laboratory study report will be transmitted to the researcher, authenticated in the study and the patient. The study investigator will enter the result reflected in the report into the clinical case registration form.

After that, the remains of the biological material sample will be destroyed according to the procedures adopted in the laboratory.

During the initial assessment and follow-up period, blood and urine samples of the study participants involved can be collected and processed by the medical care team and the study center investigator for various laboratory-diagnostic tests as part of the ongoing clinical assessments - at the end of the 3rd, 6th and 12th months and in case of early withdrawal of the participant from the study or at any time during the follow-up. These laboratory tests may be performed as routine diagnostic tests in real-world practice in an accredited diagnostic laboratory of the study center or other medical institution using conventional (generally accepted) methods for performing these tests.

The results of the tests performed in the laboratory of the study center or other medical institution within the follow-up period can be collected in the patient's outpatient medical record as a routine practice. The investigator may transfer the results of these diagnostic tests to the study case registration form and then use them for the purposes of the study.

The patient's outpatient medical record will also include the results of other laboratory tests used for routine management of the patient's condition, which are not of interest to the study, although they can be used to characterize the study's endpoints.

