#### **2.6.4 Data and Safety Monitoring**

Study data monitoring will be carried out throughout the study as part of the monitoring and evaluation activities.

The practical monitoring and evaluation activities and the structuring and processing of data will be carried out by a group formed within the framework of the management of the research project - representatives of the research centers, the sponsor and the research team.

The study sponsor will discuss the results of the study data monitoring. Because the study contains minimal risks and dangers for the study participants, but provides for double-blind randomization for the selection of the study-specific treatment interventions, includes concerns on a highly-specialized clinical practice area, considers a 12-month observation period for the study participants and may have an impact on current clinical practice monitoring process will also be cooperated by the Institutional Review Boards (IRBs) of the study centers involved.

The study monitoring and evaluation team observes study activities at study centers and assesses the safety, scientific and practical relevance, consistency and continuity of data collected. IRBs monitor and evaluate the confidentiality of data collection and management, ethical issues of clinical case management and safety at clinical centers.

The study monitoring and evaluation team consists of specialists with experience in conducting research and evaluations, data management, issuing recommendations and advice on the scientific aspects of research, who are not directly involved in the implementation of this research, do not have intellectual and financial conflicts of interest and formed preconceived ideas and biases concerning the research problem.

The functions of the study monitoring and evaluation team are to observe and evaluate the following processes:

- Involvement of research participants;
- Compliance of research procedures with the research protocol;
- Safety of collected data and their scientific processing;
- Research progress;
- Compliance of the collected data on important adverse clinical events with the clinical endpoints;
- Follow-up management needs of the trial participants;

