## 7.0 Study Records and Reports

### 7.1 Record Keeping and Data Processing

The data record form (DRF) will be filled in with the data from the study results of each study participant, the form and structure of which will be the same for all subjects and study centers.

At the study center, the data provided in the DRF will be collected and recorded by the study center investigator, who is directly involved in the study participant screening, randomization and follow-up. The study center investigator confirms the completeness, accuracy and authenticity of the entered study data by signature and date.

The principal investigator reviews, signs and dates each completed form. His signature will confirm the responsibility of the study sponsor for the completeness and relevance of the study data (clinical, laboratory, other) entered in the DRF.

The fields allocated for data recording in the DRF are structured according to the name, periods of study activities and the entry date. It provides spaces for recording clarifications, comments or conclusions. Data is entered into the form from primary sources of clinical information and medical documentation used in real-world practice.

In case of omission, non-use or inaccuracy of study data in the DRF, a record confirming their existence is checked in the primary source of data (medical record, authenticated result of the conducted examination, other source of registration of the study result, e.g., result registration journals, electronic databases). In such cases:

- If there are records in the primary data sources, they are transferred to the clinical data report form and the data are marked as "filling in the omission".
- If there are no corresponding records in the primary data sources, within a reasonable time frame (+2 weeks), it can be conducted through the corresponding examination and recording of the results in the DRF by the envisaged plan. In such a case, the data is marked as "filling in the unused".
- If there are no relevant records in the primary data sources and it is not possible to conduct the relevant examination and obtain the data within a reasonable time frame (+2 weeks) according to the research plan, "omission" is indicated in such a case.

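### The double-blind label can hold only up to allocation: treatment is open-label afterwards, and the plan does not say who classifies outcomes or whether they stay masked

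*Combined protocol and SAP*

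**What the plan says.** All references are to the combined protocol and SAP.

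- **Label.** Section 2.5.4: "The allocation of patients to the experimental and control groups will be carried out by double-blind randomization". Section 2.6.4, explaining why the site IRBs take part in monitoring, says the study "provides for double-blind randomization for the selection of the study-specific treatment interventions".
- **Who is masked, and when.** Section 2.5.4: "At this stage, the results of the randomization will be hidden from the study participants, the medical care team, and the clinical outcome assessors".
- **What follows.** The same section says that "after randomization and CYP2C19 genotyping, the results will be disclosed to the study participants and the medical care team". It does not mention outcome assessors again.
- **Who handles the genotype.** Under section 2.5.9 the laboratory report goes to the researcher and the patient, and "The study investigator will enter the result reflected in the report into the clinical case registration form".
- **Who records the data.** Under section 7.1 the data on the record form "will be collected and recorded by the study center investigator, who is directly involved in the study participant screening, randomization and follow-up". The principal investigator reviews and signs each form.
- **Who identifies and classifies events.** Sections 3.2.5 and 3.2.6 give this to the investigator or the sponsor.
- **Closest thing to event review.** Section 2.6.4 lists among the monitoring and evaluation team's tasks "Compliance of the collected data on important adverse clinical events with the clinical endpoints". It does not call this check masked and does not describe it as adjudication.

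**The concern.** Double-blind ordinarily tells a reader that neither the patient nor those treating or assessing the patient know the assignment during follow-up. This design cannot deliver that. Section 2.3.2 gives the control arm no genotype test and moves loss-of-function carriers to a different P2Y12 inhibitor, so the medical record itself reveals the arm.

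The stake is detection bias. Several endpoints in section 2.6.1 need judgement: attribution of a death to a cardiovascular cause, unstable angina, TIA, heart failure event, and the line between major and non-major bleeding. The composites inherit that judgement. Section 2.6.1 gives no criteria for major bleeding or for a heart failure event, which widens the discretion. The safeguards in section 2.5.7 (random selection, eligibility criteria, handling of confounders, monitoring) address baseline comparability and data quality. None addresses knowledge of the arm when an event is classified. A report that carried the label forward would overstate the trial's protection.

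**Working it through.** The plan states no figure on this point, so the check sets the passages side by side and then illustrates scale.

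**Step 1: what the masking statement covers.** The masking sentence in 2.5.4 is limited to the allocation stage, and the next sentence discloses results to patients and the care team. The design statements in the Synopsis and section 2.3.1 do not call the trial blinded. The label therefore attaches to randomisation. The accurate term is concealed allocation, then open-label treatment.

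**Step 2: who classifies events.** The genotype report reaches the researcher, and the study investigator enters it (2.5.9). The site investigator who screens, randomises and follows up also completes the record form (7.1). The investigator or sponsor identifies MACCE and anticipated medication effects (3.2.6) and classifies them (3.2.5). The sponsor offers no masked alternative, since its own laboratory does the genotyping (2.5.9). No section describes a masked assessor or adjudication committee.

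**Step 3: which endpoints are exposed.** Exposed: cardiovascular death, unstable angina, TIA, heart failure event, bleeding grade and the composites built on them. Patient-reported outcomes and the decision to revascularise are open-label by nature. All-cause death needs no classification. It is largely rather than wholly immune, because section 3.2.6 withdraws a participant once a MACCE or anticipated medication effect is registered, so classification can affect whose later follow-up is observed.

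**Step 4: illustration of scale.** Group sizes of 160 guided and 80 control come from section 2.4.2 (110 + 50, and 80). The 5% true rate and the miscoding counts are assumptions. With a guided and b control events, RR = (a/160)/(b/80), and SE(ln RR) = √(1/a − 1/160 + 1/b − 1/80).

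- No miscoding: 8/160 = 5% v 4/80 = 5%; RR 1.0.
- One down in guided, one up in control: 7/160 = 4.375% v 5/80 = 6.25%; RR 0.70; SE = √0.3241 = 0.569; 95% CI 0.23 to 2.14.
- Two each way: 6/160 = 3.75% v 6/80 = 7.5%; RR 0.50; SE = √0.3146 = 0.561; 95% CI 0.17 to 1.50.
- Two each way in the opposite direction: 10/160 = 6.25% v 2/80 = 2.5%; RR 2.5; SE = √0.5813 = 0.762; 95% CI 0.56 to 11.1.

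A second illustration assumes equal true rates, relative under-classification in the guided group only, and a two-sided Pearson chi-square test at 5%, with rejection rates found by exact binomial enumeration:

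- True rate 5%: 4.4% with no misclassification; 5.2%, 6.7%, 9.2% and 18.4% at 10%, 20%, 30% and 50% under-classification.
- True rate 10%: 4.8%, then 5.9%, 8.7%, 13.6% and 31.3%.
- True rate 20%: 5.0%, then 7.0%, 12.9%, 23.3% and 57.3%.

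Section 3.2.1 puts MACCE probability at 1–10%, so the first two rows are the more relevant ones for MACCE.

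**The case against.** The strongest reply is that the plan never promises masked follow-up. Section 2.5.4 confines masking to allocation and openly discloses results afterwards. This stands. A reader might infer that the plan claims masked outcome assessment throughout and then breaks the claim; the text does not support that. It is silent on later masking.

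Second, a reader might infer that the site investigator is the outcome assessor and that no masked assessor exists. No section says so. Section 2.5.4 names assessors separately from the care team and leaves them out of the disclosure list, so they could be read as staying masked. That the investigator or sponsor fills the role is an inference from 2.5.9, 3.2.5, 3.2.6 and 7.1. It is the best available reading because no other assessor is described.

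Third, a reader might infer bias in favour of guidance, because sections 2.5.8 and 3.1 say that genotype-based selection improves the chance of preventing MACCE. Those are risk-justification statements and give no instruction on coding events. Direction and size remain unknown.

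Fourth, the illustrated relative risks have intervals that include 1, and section 2.6.3 requires 95% intervals, so neither the 0.70 nor the 0.50 case would by itself support a claim of benefit. This also stands. Nor should the illustration be read as an Appendix 3 result for hospitalised angina: that appendix has rows for recurrent angina only.

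**Conclusion.** The concern holds in limited form. The double-blind wording in 2.5.4 and 2.6.4 names a property that the design cannot have after allocation, and the plan leaves open who classifies outcomes and whether they are masked. On the reading in Step 2, judgement-based endpoints, including one of the two primaries, are exposed to detection bias.

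No size can be put on that bias from the documents. The illustrations show only that, at these group sizes and an assumed 5% rate, four reclassified events can halve the point estimate, or more than double it if they run the other way, with wide intervals in both cases. The point calls for a correction of wording and a masked check. It does not show that the results will be biased.

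**What to change.** 1. In sections 2.5.4 and 2.6.4, replace double-blind randomization with: allocation concealed until randomisation; open-label thereafter. Report the trial as open-label. This costs only the edit.

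2. Have the event-versus-endpoint check in section 2.6.4 done from coded packets with arm, genotype and P2Y12 drug removed, against written event definitions. The reviewers should be existing monitoring and evaluation team members who have no site or sponsor role, do not monitor randomisation or product use, and have no access to the database or genotype for those cases. The restrictions are needed because section 2.6.4 describes the team both as representatives of centres, sponsor and research team and as people not directly involved, section 4.0 has monitoring cover randomisation and product use, and section 7.1 gives members database access.

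3. If no such members exist, make change 1 alone and report these endpoints as unmasked. In either case, report patient-reported outcomes and revascularisation as open-label.

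The cost of change 2 is writing the definitions and coordinator time for redaction. The packet count is uncertain: 1–10% of 240 is 2.4 to 24 MACCE, but that range in section 3.2.1 does not cover bleeds, for which no frequency is given.

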#### **2.5.5 Compliance with Treatment**

The study does not use new medications or treatments and does not investigate their previously unknown effects. The subject of the study is the selection of the most commonly used antiplatelet drug regimens after PCI in CAD cases in current, real-world clinical practice based on the results of CYP2C19 allele genotyping.

The use of the drugs of interest, P2Y12 inhibitors - clopidogrel or an alternative P2Y12 inhibitor, in patients with selected clinical characteristics has already been tested, studied and recommended by the European Society of Cardiology guidelines and recommendations as part of routine DAPT in patients with CAD after PCI for the prevention of recurrent MACCE events.

Thus, these drugs are prescribed and used in everyday, real-world clinical practice, even without research interests and ensure the prevention of MACCE cases of ASCVD. This circumstance is an important basis for patient motivation, study participation and adherence to treatment. In addition, other drugs are used to treat patients with selected clinical characteristics, which can be prescribed to the study group patients. Today, both the drug of interest in the study (clopidogrel) and alternative antiplatelet drugs are available for regular use, which is one additional component of treatment adherence.

The patient's informed consent form, which explains the treatment measures to be carried out within the framework of the study and the patient's formal expression of consent (signing the informed

consent form), is an important criterion for inclusion in the study and, at the same time, represents an important basis for treatment adherence.

A 12-month clinical follow-up during the treatment will also be a prerequisite to patient motivation and treatment adherence. To this end, patients will undergo clinical assessments supporting adherence and motivation to therapy during the 3rd and 6th month follow-up visits.

